4.5.8.10 Concomitant Medication and Rescue Medication

Medications will be coded using the World Health Organization Drug Dictionary, Version June 2014.

A medication will be considered concomitant if it has a start date on or after the first dose of IMP or if it was started prior to the first dose of IMP and was ongoing. If a medication has a

partial or missing start/stop date and it is unclear from the date whether the medication was taken after the first dose of IMP then it will be considered concomitant.

For summaries and listings of medications the following approach will be used to determine the Anatomical Therapeutic Chemical (ATC) term to be presented:

- If coded to level 4 then the level 4 coded term will be presented.
- If coding is not performed at level 4 but level 3 coding is present then level 3 coded term will be presented.
- If coding is not performed at level 3 but level 2 coding is present then the level 2 coded term will be presented.
- If coding is not performed at level 2 but level 1 coding is present then the level 1 coded term will be presented.

Summaries of each of the following by ATC term and preferred term will be summarized by absolute counts (n) and percentages (%):

- History of antiepileptic medications.
- Concomitant antiepileptic medications.
- Concomitant rescue medications.
- Other concomitant medications.

The ATC term, preferred term, reported generic name and reported brand name will be listed.

The start day and stop day will be included in the listing according to Section 4.1.3. If the date is partial and the exact day is unknown then the text 'pre' or 'post' will replace the start or stop day if it is clear from the partial date that the medication started or stopped prior to or after the first dose of IMP.

4.5.8.11 Growth and Development

IGF-1 levels will be analyzed as part of the clinical laboratory testing. IGF-1 levels will be summarized on a continuous scale, including change from baseline.

The pubic hair growth (both sexes), genital (males only) and breast (females only) development of all adolescent patients (i.e., 10 to less than 18 years of age at the time of signing the informed consent form, or earlier if clinically indicated by onset of menarche or other signs of precocious puberty) will be assessed using Tanner Staging. The patients will undergo a discreet physical examination and be assigned a value under each category of pubic hair growth (both sexes), genitals (males only), and breasts (females only).

Patients will be examined at Visit 1 (Day 1) and the end of treatment visit. Once a patient reaches a score of V (i.e., 5) the examination need not be performed again.

Tanner Stages will be summarized on a categorical scale.

4.5.8.12 Menstruation

Caregivers will be asked if the female patient is menstruating and details will be recorded as part of their medical history (Visit 1); any changes in normal cycles will be captured at the end of treatment visit.

Menstruation details will be summarized as appropriate, including any changes in normal cycles at the end of treatment.

4.5.8.13 Exposure to Study Medication

Patients are required to take IMP twice daily (morning and evening). The first OLE dose will be taken in the clinic on Visit 1 (Day 1). The date of final dose in the study will be recorded on the CRF. The date of final dose, for patients who enter the taper period, will be recorded on the CRF at the end of taper visit.

The total number of dosing days in the study will be calculated as:

$$(\text{Date of last dose in the treatment phase} - \text{Date of Day 1}) + 1$$

The date of last dose in the treatment phase will be obtained from the CRF at the end of treatment visit.

The total number of dosing days in the study will be summarized for all patients, and patients who completed the treatment phase. The modal dose will be calculated for each patient over the same periods associated with IVRS calls for seizure reporting and will subsequently be summarized. Furthermore, a categorical summary of patients whose largest dose was 20 mg/kg/day or less, patients whose largest dose was over 20 mg/kg/day and less than 30 mg/kg/day, and patients whose largest dose was 30 mg/kg/day or more during the OLE study will be presented.

The above summaries will be repeated for the following subgroups:

- Excluding data for patients from study GWEP1332 Part A
- Patients taking clobazam
- Patients not taking clobazam
- Core study actual treatment: GWP42003-P
- Core study actual treatment: Placebo
- Patients taking clobazam; core study actual treatment: GWP42003-P
- Patients not taking clobazam; core study actual treatment: GWP42003-P
- Patients taking clobazam; core study actual treatment: Placebo
- Patients not taking clobazam; core study actual treatment: Placebo

The modal dose for each patient will be calculated across their entire period of exposure, and the number of patients and patient-years exposure will be summarized in the following groups:

- $\leq 20\text{mg/kg/day}$
- $20 - < 25\text{mg/kg/day}$
- $\geq 25\text{mg/kg/day}$

For each group, the total number of patient-years of exposure will be calculated as the sum of the total number of dosing days for each patient divided by 365.25. For the calculation of modal dose, patients will be assumed to be taking 20 mg/kg/day unless a dose adjustment is recorded.

Any missed doses during treatment should be recorded on the 'IMP Missed Doses Log' CRF page.

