8.1.2 Dose Escalation, Dose Adjustments and Down-Titration

The titration regimen is shown in [APPENDIX 4](#). All patients will titrate up to a target dose of 10–20 mg/kg/day GWP42003-P.

Patients will be weighed at each study visit. During Visit 1, the daily volumes of IMP solution to be taken during the titration period will be calculated via the IVRS and the dosing regimen provided to the patient and/or caregiver. Patients should aim to achieve the target dose before the end of the 2-week titration period; however, Investigators may decrease the dose if a patient experiences intolerance, or increase the dose if required for better seizure control, until the optimal dose is found. The titration period will be considered 2 weeks long to ensure most patients have achieved stable dosing from Visit 2 onwards (maintenance period). The rate of titration should be adjusted based on the specific needs of an individual patient. It is advised that the Investigator considers monitoring hepatic function (ALT, AST, TBL and INR levels) during the titration period for patients taking AEDs that are known to be associated with hepatic injury or failure. To minimize any elevations in hepatic function markers the titration period can be extended and the dosage of a concomitant AED and/or GWP42003-P may be adjusted at the discretion of the Investigator. If there is intolerance during titration, the patient may be maintained on a dose below 10-20 mg/kg/day. A titration rate faster than recommended may be considered if there is an increase in seizures, following consultation with the GW medical monitor. Further information on dispensing procedures will be provided in a separate Pharmacy Manual.

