If an unacceptable AE develops at any time during titration, dosing should initially be suspended or amended, at the Investigator's discretion, as appropriate, until the event has resolved or is well tolerated. During the maintenance period, Investigators may decrease the dose if a patient experiences intolerance, or increase the dose if required for better seizure control, until the optimal dose is found. The Investigator may schedule additional clinic visits during the maintenance period to facilitate dose adjustments, e.g., when increasing doses above 20 mg/kg/day. Patients whose dose has been decreased can have their dose increased again provided there is adequate tolerance. Dose increases above 20 mg/kg/day are recommended to be done slowly, with maximum increments of 2.5 mg/kg every 5–7 days. The maximum dose patients can receive will be 30 mg/kg/day.

For patients who do not immediately continue to use GWP42003-P following the 'End of Treatment' visit, IMP will be down-titrated at home (10% per day for 10 days). Additional IMP will be dispensed, if required. Patients who withdraw early should also begin the taper period following the Withdrawal visit (unless continued dosing is not possible due to an AE). The IVRS will generate the patient's daily IMP dosing volumes for the 10-day taper period, during which time IVRS and diary information will continue to be recorded.

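### Table 10.6 assigns each patient's whole exposure to one modal-dose band, so it does not show patient-years above 20 mg/kg/day, and no other planned table gives patient-years or safety events by dose

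*SAP*

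**What the plan says.** SAP 4.5.8.13 (Exposure to Study Medication) sets the rule for Table 10.6: "The modal dose for each patient will be calculated across their entire period of exposure". Within each band, "the total number of patient-years of exposure will be calculated as the sum of the total number of dosing days for each patient". The total is converted to years of 365.25 days. Dosing days run from Day 1 to the last treatment-phase dose and take no account of dose level. The bands are printed as 20 or less, 20 to less than 25, and 25 or more. For the mode, "patients will be assumed to be taking 20 mg/kg/day unless a dose adjustment is recorded".

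The same section plans two other dose outputs. One is "a categorical summary of patients whose largest dose was 20 mg/kg/day or less", with further groups for a largest dose above 20 but below 30 and for 30 or more. The other is by period: "The modal dose will be calculated for each patient over the same periods associated with IVRS calls for seizure reporting". SAP Appendix 5 also has Listing 10.2, exposure by time.

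Dose is expected to move. Protocol 8.1.2 lets investigators reduce it for intolerance or raise it for seizure control, and adds: "Patients whose dose has been decreased can have their dose increased again provided there is adequate tolerance". Increases above 20 are recommended in steps of at most 2.5 mg/kg every 5-7 days, and "The maximum dose patients can receive will be 30 mg/kg/day". SAP Table 1 shows no Core Study arm above 20 mg/kg.

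SAP 4.1 sets the table columns as Dravet, Lennox-Gastaut and overall. In Appendix 5, the AE tables (11.1 to 12.5), laboratory tables (13.x) and vital-sign, ECG and other safety tables (14.x) have no dose split.

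**The concern.** The primary objective is long-term safety under flexible dosing. Within this extension and its Core Studies, only the extension supplies experience above 20 mg/kg/day. A reader will want to know how much person-time was spent there and what happened during it.

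Table 10.6 is the only planned table of patient-years by dose, and its rule moves all or none of a patient's time when the mode changes. A mode needs only a plurality, so a patient who spends most of follow-up above 20, spread over several dose levels, can be credited with none. The AE and laboratory tables are pooled over dose, so they cannot show which events arose above 20.

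**Working it through.** The plan states no patient-years figure, so there is nothing to reproduce. I applied the SAP rule to assumed dose histories and compared it with a day count.

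**Inputs.** Titration follows Protocol Appendix 4: below 20 on Days 1-10, and 20 mg/kg/day from Day 11. Follow-up is 104 weeks (728 days), the two-year mark in Protocol 4.1. Escalation goes from 20 to 30 in 2.5 mg/kg steps every 7 days (Protocol 8.1.2). A dose of exactly 20 goes in the lower band. The timing of dose changes is assumed, because the documents give none.

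**Formulas.**
- Credited weeks above 20 = 104 if the whole-study mode exceeds 20, otherwise 0.
- True weeks above 20 = days with dose above 20, divided by 7.

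**Individual courses (weeks above 20).**

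| Course | Credited | True |
|---|---|---|
| Escalate at week 12 | 104 | 92 |
| Escalate at week 40 | 104 | 64 |
| Escalate at week 60 | 0 | 44 |
| Escalate at week 12, back to 20 at week 60 | 0 | 48 |
| Escalate at week 12, back to 20 at week 66 | 104 | 54 |
| 22.5 at week 32, 25 at week 56, 27.5 at week 80 | 0 | 72 |

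In the last row the patient has 30.6 weeks at 20 and 24 weeks at each higher level, so 20 is the mode although 72 of 104 weeks are above it.

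**Mean error, single escalation at week T.** The mode is 30 for T up to 51 and 20 from T = 52. The absolute error is therefore T weeks for T <= 51 (104 credited, 104 - T true), and 104 - T weeks for T >= 52 (0 credited).
- T evenly over 2-12: mean error 7 weeks; credited/true = 104/97 = 1.07.
- T evenly over 2-24: mean error 13 weeks; credited/true = 104/91 = 1.14.
- T evenly over 2-104: mean error (1325 + 1378)/103 = 26.2 weeks; credited/true = 50.5/51.0 = 0.99. The total balances only because the individual errors cancel.

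**Direction in a cohort.** Assume 20% of 680 patients (136) move once from 20 to 25 during 730 days. Credited versus true patient-years above 20 are 271 versus 187 if the move falls on days 90-365, 135 versus 136 for days 90-640, and 0 versus 85 for days 365-640.

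**What the planned per-period modes would give.** Reading the periods as the 12-week intervals of SAP 4.5.9, and summing periods whose mode exceeds 20, the mean error over T = 2-104 is 3.1 weeks (maximum 7). Ties matter: SAP 4.5.8.13 has no tie rule, and in the return-at-week-66 course one period splits 42/42 days, giving 48 or 60 weeks against a true 54. A day count has no error for recorded changes.

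**Why a dose split needs time rows.** Suppose dose has no effect, 20% of person-time is above 20 and all of it after week 12, and the AE rate is k times higher in weeks 1-12 of 104. The crude rate ratio of >20 to <=20 is 0.8/(0.115k + 0.685), which is 0.87 for k = 2 and 0.78 for k = 3. An unstratified table would make higher doses look safer.

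**The case against.** The strongest reply is that Table 10.6 does what its title says: it groups exposure by modal dose, under an openly stated rule. The SAP never calls it time above 20 and divides no event count by it. Protocol 13.4 and 13.6.2.1 ask for overall and by-etiology summaries, not dose splits. All of that stands. A reader might infer that AE rates are miscalculated or that a protocol commitment is broken; the documents support neither.

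The size is also open to challenge. The 26-week figure depends on escalation being equally likely at any time. The protocol's wording about adjusting until the best dose is found fits early changes at least as well, and then the error is 7 to 13 weeks. That stands too. Late escalation and return to 20 give large errors, but their frequency is unknown.

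Other outputs partly cover the gap: largest-dose counts, modal dose by period and Listing 10.2. Time above 20 could be approximated from them, but none is planned as patient-years by dose or tied to events.

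A reader might also infer from the printed bands that patients at exactly 20 will be counted twice. The text as read does put 20 in two bands, but a greater-than sign may have been lost from the PDF. The largest-dose categories in the same section place 20 in the lower group, so the intended edge is clear. This is a wording point only.

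Finally, dose here follows seizure control and tolerability, so a full set of dose-stratified tables would be partly a matter of preference. That argues for one modest summary. Protocol 3.3.1 also cites expanded-access use above 20 mg/kg/day, so the extension is not the only experience at such doses, only the only source among these studies.

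**Conclusion.** The point holds as an inexpensive improvement to a descriptive analysis. Followed exactly, SAP 4.5.8.13 does not measure patient-years above 20 mg/kg/day for any patient whose dose crosses 20, and the planned tables do not connect safety events to dose.

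The mean error of 7, 13 or 26 weeks per patient rests on the assumed 104-week, single-escalation model and on when escalation happens. It should not be read as an estimate for this study. In particular, it does not show that Table 10.6 will overstate or understate high-dose exposure in total: the assumed cohorts gave ratios from 0 to about 1.45. No planned result becomes invalid.

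**What to change.** 1. In SAP 4.5.8.13, compute Table 10.6 patient-years by counting each dosing day at the dose then prescribed, from the recorded adjustments, in bands <=20, >20 to <25 and >=25 mg/kg/day. This also settles the edge at 20. Keep modal-dose patient counts if wanted, with the same edges.
2. Add dose at onset to the AE listing.
3. Add one descriptive summary of TEAEs, serious TEAEs and ALT/AST >=3 x ULN (the multiple in SAP 4.5.3.1) at <=20 versus >20 mg/kg/day, split by time on treatment, for example Weeks 1-2, 3-12, 13-48 and 49 onward. Classify liver values by dose at sampling, because scheduled visits are mostly 28 weeks apart after Week 48.
4. Footnote it: dose is non-randomised and confounded by seizure control and tolerability; safety calls are weekly during titration above 20 (Protocol 9.2.16), so AE capture differs; and liver findings may reflect co-medication, since Protocol 8.1.2 singles out "patients taking AEDs that are known to be associated with hepatic injury or failure".

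The cost is a little extra programming on dose, AE and laboratory records already collected. Cells above 20 may be small, and the comparison stays descriptive: the time rows do not remove selection of patients who tolerate the drug.

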4 EXPERIMENTAL PLAN

4.1 Study Design

This is a multi-center, OLE study for patients with DS or LGS who have completed the double-blind, placebo-controlled, clinical studies of GWP42003-P (Core Studies). The study consists of a titration period and a maintenance period, followed by a 10-day taper period.

Titration Period: All patients will titrate up to 10–20 mg/kg/day GWP42003-P using a recommended titration schedule (see [APPENDIX 4](#)). It is advised that the Investigator considers monitoring hepatic function (alanine aminotransferase [ALT], aspartate aminotransferase [AST], total bilirubin [TBL] and international normalized ratio [INR] levels) during the titration period for patients taking concomitant AEDs that are known to be associated with hepatic injury or failure. To minimize any elevations in hepatic function markers the titration period can be extended and the dosage of a concomitant AED and/or GWP42003-P may be adjusted at the discretion of the Investigator. If there is intolerance during titration, the patient may be maintained on a dose below 10–20 mg/kg/day. A titration rate faster than recommended may be considered if there is an increase in seizures, following consultation with the GW medical monitor.

Maintenance Period: Patients will continue dosing at 10–20 mg/kg/day. However, Investigators may decrease the dose if the patient experiences intolerance, or increase the dose if required for better seizure control, until the optimal dose is found. The Investigator may schedule additional clinic visits to facilitate dose adjustments e.g., when increasing doses above 20 mg/kg/day. Patients whose dose has been decreased can have their dose increased again provided there is adequate tolerance. The maximum dose patients can receive will be 30 mg/kg/day (51 mg/kg/day is the maximum dose safely used in the USA EAP to date with a mean dose of 24 mg/kg/day [$n = 59$]). Dose increases above 20 mg/kg/day are recommended to be done slowly, with maximum increments of 2.5 mg/kg every 5–7 days. If seizure freedom is achieved with use of GWP42003-P during the study, the Investigator can consider reducing the dose of concomitant AEDs after consultation with the GW medical monitor.

Study Completion: The maximum duration of this OLE study will be 4 years (208 weeks after Visit 1).

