13.1 Sample Size, Power and Significance Levels

As this is an open label safety study, there is no formal sample size calculation. All patients who wish to continue on IMP from the populations included in the double-blind Phase 2 and Phase 3 Core Studies in DS and LGS will be eligible for inclusion. Approximately 680 patients will be enrolled.

All data collected during this study will be summarized across time, using appropriate descriptive statistical methods. There will be no formal hypothesis testing.

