3.1.1 Titration Period

When patients have completed the core study from which they enter this study, they may either be receiving Placebo (of varying dose), 5 mg/kg/day GWP42003-P, 10 mg/kg/day GWP42003-P or 20 mg/kg/day GWP42003-P as per their original allocation in their respective core study. Upon entering this study, patients will titrate to 20 mg/kg/day

GWP42003-P using a recommended titration schedule during the 2-week titration period to achieve a stable dose prior to entering the maintenance period.

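### The SAP's default modal dose of 20 mg/kg/day does not match the protocol's 10–20 mg/kg/day range and, as printed, falls in two modal-dose groups

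*SAP*

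**What the plan says.** Protocol 8.1.2 has patients "titrate up to a target dose of 10–20 mg/kg/day", and Protocol 4.1 says of maintenance: "Patients will continue dosing at 10–20 mg/kg/day". A patient who does not tolerate titration may be kept below that range. The schedule in Protocol Appendix 4 nevertheless runs up to 20 mg/kg/day, reached on Day 11.

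The SAP describes a single value. Section 3.1.1 states "Upon entering this study, patients will titrate to 20 mg/kg/day", and section 3.1.2 continues maintenance at the same dose. SAP 4.7, which lists departures from the protocol, does not mention the difference.

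SAP 4.5.8.13 uses modal dose in two ways:

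- It is calculated per patient over the seizure-reporting periods and summarized. The exposure summaries are then repeated for nine subgroups (SAP Appendix 5, Tables 10.2 to 10.5.4).
- It is calculated over the whole exposure, and patients and patient-years are tabulated in three groups, printed as ≤20, 20 to <25 and ≥25 mg/kg/day (Table 10.6).

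The default is "patients will be assumed to be taking 20 mg/kg/day unless a dose adjustment is recorded". The same section also classifies patients by largest dose: 20 or less, over 20 and below 30, and 30 or more. Those categories do not overlap.

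**The concern.** The default fills in one end of a range that the protocol leaves open. A patient who stops titrating at 10 or 15 is on target under the protocol. If the stop is not entered as an adjustment, the SAP reports that patient at 20. The default value is also the only dose that belongs to two of the printed groups, so the rule sends patients to the one point where the grouping is undefined.

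At stake is the accuracy of the descriptive exposure tables by dose, in a study whose primary objective is long-term safety and tolerability. A reader who uses those tables to judge how much experience exists at a given dose could be misled about the modal dose by period and about the split between the two lower groups.

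**Working it through.** There is no sample-size or power figure to reproduce: "As this is an open label safety study, there is no formal sample size calculation". The planned enrolment of about 680 (Protocol 13.1) is used below only to show scale.

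**1. Groups as printed.** Put doses through ≤20, 20 to <25 and ≥25:

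| Modal dose (mg/kg/day) | Group(s) met |
|---|---|
| 10, 12.5, 15, 17.5 | ≤20 |
| 20 | ≤20 and 20 to <25 |
| 22.5 | 20 to <25 |
| 25, 30 | ≥25 |

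Only 20 is ambiguous. If the middle group is read as >20 to <25, each dose falls in exactly one group. Every dose from 10 to 20, and the default itself, then falls in ≤20.

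**2. Default against true modal dose.** I take the periods to be the 12-week (84-day) periods of SAP 4.5.9, and I read the default as covering every modal-dose calculation. Over Days 1–84 of Appendix 4:

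- Full schedule: Days 11–84 at 20, so 84 − 10 = 74 days. The mode is 20 and the default is right.
- Stopped at 10 from Day 7: 84 − 6 = 78 days at 10. The mode is 10 and the default gives 20; 20/10 = 2.0 times.
- Stopped at 15 from Day 9: 84 − 8 = 76 days at 15. The mode is 15 and the default gives 20; 20/15 = 1.33 times.
- Leaves before Day 11 on schedule: never received 20, but is reported at 20 if no adjustment is recorded.

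**3. Effect on the mean.** Let s be the share of patients settled at dose d below 20 with no recorded adjustment, and take the rest at 20. The mean is overstated by s × (20 − d). The documents do not give s, so a range is assumed:

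| s | d = 15 | d = 10 |
|---|---|---|
| 0% | 0 | 0 |
| 10% | 0.10 × 5 = 0.5 | 0.10 × 10 = 1.0 |
| 25% | 0.25 × 5 = 1.25 | 0.25 × 10 = 2.5 |
| 50% | 0.50 × 5 = 2.5 | 0.50 × 10 = 5.0 |

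Units are mg/kg/day.

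**4. Effect of the overlap.** Assume N = 680, a share at exactly 20 of 30%, 50% or 70%, and the rest split equally between below 20, >20 to <25, and ≥25.

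| Share at 20 | Patients at 20 | Sum of groups if 20 counts twice | ≤20 group with 20 in it | ≤20 group without 20 |
|---|---|---|---|---|
| 30% | 204 | 680 + 204 = 884 | 363 | 159 |
| 50% | 340 | 680 + 340 = 1020 | 453 | 113 |
| 70% | 476 | 680 + 476 = 1156 | 544 | 68 |

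Example for the first row: (0.70/3) × 680 ≈ 159 patients are below 20, and 159 + 204 = 363.

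**The case against.** The strongest reply is that early stops may well be recorded. The only written schedule goes to 20, so stopping at 10 departs from it, and Protocol 8.1.2 treats dose changes in the same section as escalation. The SAP says it was prepared from the protocol and the case report form, which is not available here. If that form logs an early stop as an adjustment, the default never touches the patient. This stands: the documents show that the capture rule is unstated, not that lower doses go unrecorded.

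The overlap may also be no more than a missing character. The largest-dose categories in the same section use over 20, which makes >20 to <25 the likely intention, and a lost symbol in the text conversion cannot be excluded. That would settle the groups but leave the default as it is.

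A reader might infer that patient-years are credited to the wrong dose, or that the denominator of the safety conclusions is wrong. The documents do not support either. Once the overlap is removed, the default moves no patient whose true dose is 20 or less out of ≤20. The period-level summary carries no patient-years. No adverse event summary in SAP 4.5.2 or Tables 11.1 to 12.5 is by dose.

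**Conclusion.** The point holds in a limited form. Modal dose by period, with its subgroup repeats, is overstated for any patient kept below 20 without a recorded adjustment (2.0 times at 10, 1.33 times at 15) and for patients who leave before reaching 20. As printed, counts and patient-years by modal-dose group are not uniquely defined at 20, the default value.

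Total dosing days and overall patient-years do not use the default, the largest-dose categories are not said to use it, and adverse event tables do not depend on it. It would therefore go too far to say that exposure by dose will be wrong. How much is wrong depends on how many patients stayed below 20 with no adjustment entered. The documents do not give that number, and it could be zero. The mean shifts and group totals above rest on assumed shares and show scale only.

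**What to change.** - Derive modal dose from recorded dosing: IMP use in the daily paper diary (Protocol 9.1.12), dose records on the case report form, and weight at each visit. State that a titration stopped below 20 counts as a recorded dose.
- Where no dose is recorded, use a missing-dose category, or show the 20 mg/kg/day assumption only as a labelled sensitivity summary.
- Write the middle modal-dose group as >20 to <25, in line with the largest-dose categories.
- Reconcile Protocol 4.1 and 8.1.2 with SAP 3.1.1 and 3.1.2 on the target and maintenance dose. This review takes no position on which description is right.

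The cost is SAP wording, some extra derivation work, and some patients with a missing modal dose. Two checks come first. The documents describe IVRS-calculated volumes only for titration and taper, and they do not show that daily diary doses reach the analysis database. Splitting the ≤20 group to show the lower part of the range would be a presentation choice and is not needed to correct the figures.
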